3.3. The safety population

The safety population includes all enrolled patients who received at least one dose of study drug. All safety analyses will be evaluated using the safety population.

G1 Therapeutics

4. GENERAL CONSIDERATIONS FOR DATA SUMMARY AND DISPLAY

4.1. Treatment Group Descriptions and Display in Table, Listings and Figures

This is a single-arm study in which all patients are treated with Trilaciclib + Sacituzumab govitecan-hziy. For TLFs that will be generated following SAP execution, the term *overall* will be used to describe all patients in the populations defined in Section 3.

4.2. Data Summary and Precision

General Principles of Data Summary

Data will be summarized for the respective analysis populations described in Section 3 in table format. All summary tables will only include an overall column for patients. In general, continuous variables will be summarized descriptively, i.e., the following summary statistics will be presented:

- Number of patients with non-missing data (indicated by n)
- Mean and standard deviation
- Median
- Q1 (first quartile) and Q3 (third quartile)
- Minimum and maximum values.

Categorical variables will be summarized categorically, i.e., number (n) and percentage of patients in each category will be presented.

General Principle of Data Listings

All collected data and derived variables will be included in patient data listings. An indicator will be provided for any imputed data element (e.g., imputed adverse event [AE] onset date). Columns in listings will be ordered by study site, patient ID, visit, and assessment or event date, if applicable, and then data elements.

General Principles of Precision for Summary Statistics and Calculated Statistical Quantities

The precision of summary statistics for continuous variables, including mean, median, Q1, Q3 minimum, and maximum, will be consistent with the precision of the variable as collected unless the collected data are integers. When the collected data are integers (whole numbers), the summary statistics of mean, median, Q1 and Q3 will be presented in the format with an additional digit after the decimal point. Calculated quantities of variability (e.g., standard deviation, standard error [SE]) will be presented with one more decimal place than the precision of the variable that is collected. The boundaries of a confidence interval (CI) will keep the same precision as the point estimate. The estimated adjusted relative risk will be reported with two decimal places.

For percentages, the total digits will be 3. That is, when the percentage has 2 digits prior to the

decimal point, there will only be 1 decimal place (e.g., 30.5%); while for a percentage that has only 1 digit prior to the decimal point, 2 digits places will be presented after the decimal point (e.g., 0.16%).

Rounding will take place after all calculation steps are completed prior to result display.

4.3. Definitions for Analysis Related Timepoint and Time Interval

Timepoint and time intervals related to efficacy and safety data collected during the treatment period will be summarized. For each specific category of data, the time interval by which the data will be analyzed or summarized will be specified in the respective section in which the data analysis plan is described.

To clarify data inclusion for each time interval of interest and baseline or end values for each given time interval, Table 3 presents definitions for timepoints, timepoint related assessments, and time intervals involved in statistical data analysis or summary.

Table 3Definitions for Timepoints, Timepoint Related Assessments and Time
Intervals

Term	Definition
Start of study (date)	Date of first dose of any study drug
Study baseline (assessment)	The last non-missing value prior to or on the date of the first dose of any study drug at the time that is before the time of the first study drug administration. If the event occurs on the same day as date of first dose of study drug but does not have the exact time captured, the event is assumed to have occurred prior to the first dose of study drug.
Day 1 of Cycle X (date)	The date when the first dose of any study drug for cycle X is administered. Day 1 of Cycle 1 (C1D1) is the same as the start of study.
End of a cycle (date)	It is defined as Day 1 of the subsequent cycle if the cycle is not the last cycle. For the last cycle, it is defined as the date of the End of Treatment Visit (ETV). If the ETV does not occur for a patient, End of the last cycle will be defined as 14 days post the last dose of any study drug.
Duration of a cycle (days)	Total number of days from Day 1 of the cycle to End of the cycle. That is, End of the cycle $-$ Day 1 of the cycle $+$ 1.
Duration of study drug exposure (weeks)	The total number of weeks from Day 1 of Cycle 1 to the End of the last cycle in the study. That is, (End of the last cycle –Day 1 of Cycle $1 + 1$) / 7.
Duration of total follow-up (months)	The total number of months from Day 1 of Cycle 1 to either the date of death or last contact date in the study known alive, inclusive. That is, duration of total follow-up=(date of death or date of last contact date known alive – Day 1 of Cycle $1 + 1$)/30.4375.

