#### 11.5. End of Treatment Visit

When a patient permanently discontinues study treatment, the patient should complete an End of Treatment Visit 14 days (±7 days) from last dose of study drug as outlined in Table 6.

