7.1. Duration of Study Drug Exposure

Duration of study drug exposure (weeks) is defined as the duration from Day 1 of Cycle 1 to the End of cycle for the last cycle. That is, duration of drug exposure (weeks) = (End of cycle for the last cycle in the study – Day 1 of Cycle 1 + 1)/7, where the definitions for End of cycle for the last cycle and Day 1 of Cycle 1 are provided in Table 3.

The duration of study drug exposure will be summarized at the final analysis. The total number of cycles that a patient received will be summarized as a continuous variable, as well as a categorical variable. That is, descriptive summary statistics will be provided for the total number of cycles that patients received, and the number and percentage of patients that received exactly 0, 1, 2..., to the maximum number of cycles will also be summarized.

Corresponding data listings will be provided.

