7.2. Cumulative Dose and Dose Intensity

Dose administration parameters will be summarized at the final analysis.

The definitions for cumulative delivered dose, delivered dose intensity, relative cumulative dose, and relative dose intensity at the patient level, along with other parameters involved in the calculation of these variables are presented in Table 4. All collected dose information will be used in the calculation.

The calculated cumulative delivered dose, delivered dose intensity, relative cumulative dose, and relative dose intensity will be summarized as continuous variables.

All variables described in Table 4 will be included in the data listing except for the study drug administration schedule.

G1 Therapeutics

Parameter	Meaning	Trilaciclib	Sacituzumab govitecan-hziy
Study drug administration schedule	Drug dose and schedule per protocol	240 mg/m ² IV on Day 1 and Day 8 of a 21-day cycle	10 mg/kg IV administered on Day 1 and Day 8 of each 21-day cycle.
Cumulative delivered dose [Unit]	Sum of doses over the duration of the study drug administration	Sum of doses over the duration of trilaciclib administration [mg/m ²]*	Sum of doses over the duration of sacituzumab govitecan-hziy administration [mg/kg]
Delivered Dose Intensity [Unit]	Cumulative dose administered per week	Cumulative dose (mg/m ²) / duration of study drug exposure in weeks [(mg/m ² /week)]	Cumulative dose (mg/kg) / duration of study drug exposure in weeks [(mg/kg/week)]
Relative cumulative dose (%)	Cumulative delivered dose over cumulative prescribed dose	[Cumulative delivered dose (mg/m ²) / (240 × 2 × number of cycles) (mg/m ²)]*100	[Cumulative delivered dose (mg/kg) / (10 × 2 × number of cycles) (mg/kg)]*100
Relative dose intensity (%)	Delivered dose intensity over prescribed dose intensity	[Delivered dose intensity/(480/3)]*100	[Delivered dose intensity/20/3]*100

Table 4Dose Administration Parameters for Study G1T28-213

* Actual doses administered were collected in unit of mg on the eCRF. For calculation of cumulative delivered dose and delivered dose intensity, the actual dose administered at any visit will be derived as actual dose (mg) divided by BSA (m2) from the same visit. If BSA value from a visit is missing, it will be imputed as BSA from the previous visit. If BSA value from C1D1 is missing, it will be imputed as BSA from Screening Visit. If BSA from Screening Visit and C1D1 are both missing, BSA value at C1D1 will be imputed as 1.7 m2.

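### Study drug exposure ends at the End of Treatment Visit, so relative dose intensity moves with the visit date, strongly in patients with few cycles

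*SAP*

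**What the plan says.** **End of a cycle.** For a cycle that is not the last, SAP section 4.3, Table 3 says: "It is defined as Day 1 of the subsequent cycle if the cycle is not the last cycle". For the last one: "For the last cycle, it is defined as the date of the End of Treatment Visit (ETV"). The fallback, counted from the final administration of either drug, is: "If the ETV does not occur for a patient, End of the last cycle will be defined as 14 days post the last dose of" [...].

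**Exposure.** Table 3 defines it as "The total number of weeks from Day 1 of Cycle 1 to the End of the last cycle in the study", and section 7.1 repeats this, again running to the close of the final cycle: "Duration of study drug exposure (weeks) is defined as the duration from Day 1 of Cycle 1 to the End of cycle for the last" [...]. Both give one formula: end of last cycle minus Cycle 1 Day 1, plus 1, divided by 7.

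**Dose intensity.** In section 7.2, Table 4, delivered dose intensity is cumulative dose divided by "duration of study drug exposure in weeks". Relative dose intensity compares this with a prescribed intensity of 480/3 for trilaciclib and 20/3 for sacituzumab govitecan, that is, two planned doses per 3 weeks. The same table defines relative cumulative dose, which divides delivered dose by planned dose times number of cycles and uses no dates.

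**Visit timing.** Protocol section 11.5: "the patient should complete an End of Treatment Visit 14 days (±7 days) from last dose of study drug". A compliant visit can therefore fall anywhere from 7 to 21 days after the last dose.

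**Cycle length.** Table 3 has a separate row, duration of a cycle: "Total number of days from Day 1 of the cycle to End of the cycle", computed as end minus Day 1 plus 1.

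**The concern.** The numerator of dose intensity stops at the last dose. The denominator runs on to a visit whose date has nothing to do with drug delivery, while the reference assumes a fixed 3 weeks per cycle. Two patients with identical dosing can therefore get different relative dose intensities, and an early visit can give more than 100% with no extra drug.

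The effect is largest in patients with few cycles, who are those stopping early. With 30 patients enrolled (SAP section 1.1) and the mean, standard deviation, minimum and maximum all reported (section 4.2), a few such patients can visibly shift the table. There is no control arm to share the artefact. Delivery also matters to the argument for trilaciclib: protocol section 4.2.1 lists maintained chemotherapy dose intensity in its anti-tumor rationale, and section 4.4 uses relative dose intensity to interpret toxicity in an earlier trial.

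**Working it through.** **Inputs.** Doses of 240 mg/m² and 10 mg/kg on Days 1 and 8 of 21 days (SAP Table 4). Exposure formula from SAP Table 3 and section 7.1. Visit at *e* = 7, 14 or 21 days after the last dose (protocol section 11.5). The number of cycles *n* is assumed, because the documents give no distribution. The sacituzumab govitecan reference is read as 20/3; Table 4 prints that cell without the inner brackets, which is a separate matter.

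**The plan's own reference.** 240 × 2 / 3 = 160 = 480/3 mg/m²/week, and 10 × 2 / 3 = 20/3 mg/kg/week. Both reproduce.

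**Full, on-time dosing.** The last dose falls on Day 8 of cycle *n*, so

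exposure days = 21(*n* − 1) + 8 + *e*

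relative dose intensity = [480*n* / (days/7)] / 160 × 100 = 21*n* / days × 100.

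The sacituzumab govitecan formula reduces to the same expression. The right answer is 100% throughout.

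| Cycles | Visit at 7 days | Visit at 14 days | Visit at 21 days |
|---|---|---|---|
| 1 | 21/15 = 140.0% | 21/22 = 95.5% | 21/29 = 72.4% |
| 2 | 42/36 = 116.7% | 42/43 = 97.7% | 42/50 = 84.0% |
| 4 | 84/78 = 107.7% | 84/85 = 98.8% | 84/92 = 91.3% |
| 6 | 126/120 = 105.0% | 126/127 = 99.2% | 126/134 = 94.0% |
| 8 | 168/162 = 103.7% | 168/169 = 99.4% | 168/176 = 95.5% |

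At the nominal 14 days, exposure is 21*n* + 1 days, one day more than planned.

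**One cycle, Day 8 dose missed.** Half the planned dose is given and the last dose is on Day 1, so exposure is 1 + *e* days and relative dose intensity is 10.5/(1 + *e*) × 100. This gives 10.5/15 = 70.0% with the visit at 14 days and 10.5/8 = 131% at 7 days. Relative cumulative dose in the same table gives 50%. If no dose is given early, relative dose intensity should not exceed relative cumulative dose; here it does, because the denominator shortens along with the missed dose.

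**Duration of a cycle.** For an on-time cycle the end is Day 1 + 21, so end minus Day 1 plus 1 is 22 days, and each boundary day belongs to two cycles. Table 4 does not use this row. For six on-time cycles with the visit at 14 days, the exposure span is 127 days, not 6 × 22 = 132.

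**Check of the proposed end date** (later of Day 1 of the last cycle + 20 and last dose + 13):

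- Full on-time dosing: Day 8 + 13 days is Day 1 + 20, so exposure is 21*n* days and the result is 100% for every *n*, whatever the visit date.
- One cycle, Day 8 missed: 21 days, 10.5/21 = 50%, equal to relative cumulative dose.
- One cycle, second dose given on day 22, a delay that the protocol synopsis and section 9.3 permit: exposure is 22 + 13 = 35 days, 21/35 = 60%. The current rule with the visit at 14 days gives 21/36 = 58.3%. Ending at Day 1 + 20 alone would give 21/21 = 100% and hide the delay.

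**The case against.** The strongest reply is that the measure works tolerably as written. The numerator is delivered dose, and Day 8 plus the nominal 14 days comes to almost exactly a planned cycle. The no-visit fallback uses the same 14 days. Real changes in delivery still show: with six cycles and the visit at 14 days, a one-week delay of every later cycle gives 126/162 = 77.8%, and a 25% sacituzumab govitecan reduction from cycle 2 gives 78.5%. The extreme figures need a one-cycle patient and a visit at the edge of the window. The missed Day 8 dose is visible in relative cumulative dose, and section 7.3 summarizes reductions, delays and interruptions separately. All of this stands, and it limits the size of the problem. It does not remove it, because compliant visits still give values that are wrong for the dosing received.

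A reader might infer two stronger points that the documents do not support. One is that the 22-day cycle count depresses dose intensity in every cycle. It does not: exposure is one span with a single added day. Summing 22-day cycles would give 95.5% at every *n*, whereas the SAP's formula gives 95.5% at one cycle and 99.2% at six with a 14-day visit. The other is that dose intensity reflects the visit date instead of the drug delivered. It reflects both, and the visit's share shrinks as cycles accumulate.

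**Conclusion.** The rule as written gives wrong relative dose intensities for both drugs whenever the End of Treatment Visit departs from its nominal date. Across the permitted window, full on-time dosing reads 72.4% to 140.0% at one cycle, 84.0% to 116.7% at two and 95.5% to 103.7% at eight. At the nominal visit the error is 4.5 points at one cycle and 0.8 at six. Its weight in the reported summaries depends on how many patients stop early, which the documents do not say. The figures assume on-time dosing, a visit inside the window and 20/3 as the sacituzumab govitecan reference.

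The 22-day cycle duration is a separate counting error in Table 3 that leaves dose intensity untouched. Nor should a reader carry this point over to efficacy: PFS, OS and response do not use the exposure span, and the dose-modification rates in Table 7 are per 100 cycles. This is worth correcting as a definition in descriptive exposure summaries, no more.

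**What to change.** 1. In SAP Table 3 and sections 7.1 and 7.2, define a separate exposure end date for delivered and relative dose intensity only: the later of Day 1 of the last cycle + 20 days and the last dose of any study drug + 13 days.
2. Keep the visit-based end date for the safety treatment period (section 9.1), concomitant medications (section 5.4) and assignment of G-CSF to cycles (section 8.1.4.1), and state which date each analysis uses.
3. Define the end of a cycle that is not the last as the day before Day 1 of the next cycle. An on-time cycle then lasts 21 days and no day belongs to two cycles.

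The cost is one extra derivation and a few lines of SAP text, with two end-of-last-cycle dates to carry and label. No data collection or visit schedule changes.

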4.4. Study Day

Study Day will be calculated for an event date or an assessment date relative to date of first dose of any study drug to provide additional information for interpretation of the event occurrence. Study Day is calculated as:

- The start date of the event (visit date, onset date of an event, assessment date etc.) date of first dose of any study drug + 1, if the event occurred on or after the date of first dose of any study drug. The day of first dose of any study drug will be Study Day 1.
- The start date of the event (visit date, onset date of an event, assessment date etc.) date of first dose of any study drug, if the event occurred prior to the date of first dose of any study drug. The day before the date of first dose of any study drug will be Study Day -1.

4.5. General Principles of Missing Data Handling

In general, the observed data are used for analyses or data summaries. That is, no missing imputation will be performed. However, imputation of missing onset or stop dates for AE and concomitant medication will be adapted to determine the status of each AE and the prior/concomitant/subsequent status of each non-study treatment medication. Please refer to Section 9.2.2 for the rules of imputation of missing AE onset or stop date and Section 5.4 for the rules of imputation of missing concomitant onset or stop dates.

For demographic and baseline characteristics, continuous variables will be summarized based on non-missing observations with the number of patients with non-missing data indicated. For a categorical variable with missing data, a category of "Missing" will be included as a separate category for the summary. That is, the number and percentage of patients in each category of the variable (including "Missing") will be summarized and reported with the number of patients in the FAS population as the denominator for the percentage calculation.

For primary and secondary efficacy endpoints, handling of missing data is described in Section 8.3.

5. DISPOSITION AND BASELINE CHARACTERISTICS

5.1. Patient Disposition

A summary of patient disposition will be generated using all accumulated data as of the database lock date.

Patient disposition summary will include the following 4 major sections:

- 1. Disposition of all screened patients who signed informed consent
- 2. Study drug disposition for patients in the safety population
- 3. Study disposition for patients in the FAS
- 4. Deaths among patients in the FAS

The specific details for each section are described below.

1. Disposition of all screened patients

The total number of screened patients who signed informed consent will be presented as two mutually exclusive groups: those who were screen failures and those who were enrolled. For those in the FAS, patients who received at least one dose of any study drug and those who did not are further presented. Unless otherwise stated, the number of patients in the FAS will be the denominator for calculating percentages of patients in each of these categories.

2. Study drug disposition

The disposition for each study drug (trilaciclib and sacituzumab govitecan-hziy) will be summarized for those who have discontinued the study drug. For patients who have discontinued the study drug, the primary reasons for study drug discontinuation will be presented with the percentage of patients in each reason being calculated based on the number of patients who discontinued the study drug.

3. Entered Survival Follow-up

The number and percentage of patients who entered survival follow-up during the study will be summarized. The number of patients in the FAS will be the denominator for the percentage calculation.

4. Study disposition

The number and percentage of patients who discontinued from the study will be summarized. The number of patients in the FAS will be the denominator for the percentage calculation. The primary reason for study discontinuation will also be summarized, and the number of patients who discontinued the study will be the denominator for the percentage calculation for each reason of discontinuation.

5. Death

The number and percentage of patients who died during the study will be summarized overall for the FAS along with the primary reason of death (Progressive Disease, Adverse Event, Other). The number of patients in the FAS will be the denominator for calculating percentages of death,

G1 Therapeutics

and the number of patients who died will be the denominator for calculating the percentage of patients within each reason for death.

A summary of enrollment status of all screened patients will also be presented by site.

Study drug and study disposition information will be provided in data listings for all enrolled patients.

5.2. Demographics and Baseline Disease Characteristics

Demographics and baseline disease characteristics will be summarized for the final analysis.

Demographics including age at screening visit, age group (18-65, > 65), sex at birth, childbearing potential, ethnicity, and race will be summarized for all enrolled patients. In addition, BMI, BSA and Eastern Cooperative Oncology Group (ECOG) score will be summarized. Further, baseline disease characteristics such as stage at screening and at diagnosis, histopathological grade and type at diagnosis, BRCA mutation, TNBC status, and PD-L1 status will be summarized for the FAS.

Data listing for demographics and baseline disease characteristics will be provided for the FAS.

5.3. Medical/Surgical History and Ongoing Conditions

Medical history, surgical history, and ongoing conditions at the Screening Visit will be summarized for the final analysis.

Non-breast cancer related medical history and ongoing medical conditions as collected at baseline will be coded using Medical Dictionary for Regulatory Activities (MedDRA) version 26.1 or later, and then summarized. Medical history and ongoing conditions will be presented by system organ class (SOC) and preferred term (PT) with SOC and PT all sorted in descending frequency based on the overall column. A patient will only be counted once within a particular SOC (PT) even if the patient has multiple conditions/diseases in the same SOC (PT).

In addition, a data listing for medical history and ongoing medical conditions collected at the Screening Visit will be provided for the FAS. Furthermore, a data listing for prior surgerical procedures and radiotherapies will be generated for the FAS.

